2.1.2.2 Pharmacodynamics

Blood, hair, and tissue samples were collected and analyzed for various biomarker assessments in a Lilly-sponsored trial of prexasertib. These assessments included circulating plasma DNA concentrations, circulating tumor cells, phosphohistone 2AX, and cytokeratin 18. However, due to variability in the clinical pharmacodynamic (PD) data and the corresponding lack of statistically significant changes, these assessments were not used to inform dose selection. Because the magnitude and duration of pCHK1 inhibition associated with the recommended phase 2 dose of 105 mg/m² in humans is not known, human PD profile simulations after administration of 105 mg/m² were generated by linking the human population PK model to the murine single-agent PK/PD indirect response model (that is, they assume a similar PD response in humans as that characterized in murine xenografts). Simulation results of the predicted median human percentage pCHK1 profile demonstrate that the average percentage pCHK1 inhibition over the first 72 hours of Cycle 1 after 105 mg/m² is 41.7% (90% CI: 25.0% to 59.5%). The predicted average percentage pCHK1 inhibition over the first 72 hours following administration of 105 mg/m² once every 14 days approaches the average percentage pCHK1 inhibition of 49.7% (90% CI: 45.0% to 54.7%) over the first 72 hours following prexasertib administration described for the minimum tumor response in nonclinical xenograft models. However, the predictive capability of this approach has limitations given the differences between animal models and humans (e.g., protein binding, tumor size/location, target expression, immune system, and prior therapies in humans). As a result, the specific magnitude and duration of pCHK1 inhibition required for optimal clinical activity are currently not known.

2.1.2.3 Clinical Metabolism

Exploratory analysis (non-radiolabeled) of plasma and urine samples collected from 3 patients following the administration of a single 50 mg/m² dose of prexasertib showed the presence of prexasertib as the major entity (prexasertib appeared as the peak with the most intense mass spectrometric response) in both plasma as well as urine, along with multiple minor oxidative and glucuronide metabolite peaks.

2.1.2.4 Clinical Drug Interactions

The potential for drug interactions was evaluated in human liver microsomes. Prexasertib (LY2606368) exhibited *in vitro* potential for competitive inhibition of CYP1A2 ($K_i = 1.6 \mu\text{M} = 767 \text{ ng/mL}$) and of CYP2D6 ($K_i = 2.8 \mu\text{M} = 1343 \text{ ng/mL}$). There was no inhibition of CYP2C8, CYP2C9, CYP2C19, CYP2B6, or CYP3A4 over a range of concentrations (0.103 - 25 μM). Furthermore, potential time-plus nicotinamide adenine dinucleotide phosphate (NADPH)-dependent inhibition by prexasertib was not observed for any CYPs over the concentration range tested (0.103 to 25 μM).

Simulations of human PK profiles that were performed using a dynamic physiologically based pharmacokinetic (PBPK) model (SimCYP®), suggest that the potential for a clinical drug interaction is minimal. More specifically, simulations of drug-drug interaction (DDI) studies with prexasertib and sensitive CYP2D6 probe substrates (desipramine and dextromethorphan) did not predict any clinically significant DDIs with either substrate. The increase in CYP2D6 substrate AUC and C_{max} ratios were < 1.2 for both substrates at the recommended prexasertib phase II dose of 105 mg/m^2 , when administered either as a single dose or following daily administration over three consecutive days.

Similarly, human simulations of DDI studies with prexasertib and sensitive CYP1A2 probe substrates (phenacetin and theophylline) did not predict any clinically significant DDIs with either one of the substrates. The increase in CYP1A2 substrate AUC and C_{max} ratios were < 1.2 for both substrates at the highest proposed prexasertib phase II dose of 105 mg/m^2 , when administered either as a single dose or following daily administration over three consecutive days.

The effect of prexasertib on CYP mRNA levels was evaluated using cryopreserved human hepatocytes from a single donor. There was no induction of CYP1A2, CYP2B6 or CYP3A4 mRNA observed at concentrations corresponding to current clinical C_{max} concentrations. However, concentration dependent down regulation of CYP3A4 mRNA was observed *in vitro* with no loss or change in CYP3A4 activity. The mechanism of this modulation and its clinical relevance has not been evaluated. The likelihood of this finding manifesting *in vivo* is further minimized given the bi-weekly dosing regimen.

The relative contributions of microsomal CYP-mediated clearance of prexasertib was studied *in vitro* using a panel of recombinant human cytochrome P450s (rCYPs): rCYP1A2, rCYP2B6, rCYP2C8, rCYP2C9, rCYP2C19, rCYP2D6, rCYP2E1, rCYP2J2, rCYP3A4, and rCYP3A5. Based on a substrate depletion approach, CYP1A2, CYP2D6, and CYP2J2 are responsible for 88%, 9.6% and 2.8% of hepatic CYP-mediated clearance of prexasertib, respectively, with other CYPs not appearing to be involved in the metabolism of prexasertib. Although CYP1A2 seems to be the major CYP involved in the *in vitro* clearance of prexasertib, the relative contributions of other non-CYP elimination pathways as well as the *in vivo* clearance pathways have not been evaluated.

Overall, *in vitro* data showed that prexasertib was 63.1 to 65.3% protein-bound in human plasma over the concentration range of 0.5 to 50 μM and 48.8 to 54.6% protein-bound in human liver

microsomes over the concentration range of 1 to 10 μM .

2.1.2.5 Clinical Safety Evaluation of Prexasertib

Please refer to the prexasertib IB for complete safety background information. Neutropenia has been the most frequent and severe toxicity after treatment with 105 mg/m² prexasertib every 14 days. Grade ≥ 4 decreases in neutrophils deemed related to prexasertib treatment have been observed in 57.7% of patients. In general, neutrophil counts reach nadir on approximately Day 8, and Grade 4 decreases are often transient (e.g., less than 5 days). Febrile neutropenia has been reported in 10.8% of patients, but no patients have discontinued or died because of febrile neutropenia. Related Grade ≥ 4 decreases in platelets have been observed in 5.2% of patients, and 3 patients (1.4%) had clinically significant bleeding (epistaxis and hematochezia) in the setting of thrombocytopenia. No patients experienced Grade ≥ 4 anemia deemed related to prexasertib treatment.

Non-hematologic toxicity occurs at a lower frequency than hematologic toxicity and has been predominantly Grade 1 or 2 in severity. Fatigue and nausea are the only non-hematologic AEs that are considered to be related to study drug treatment occurring in more than 10% of patients. The non-hematologic treatment-emergent AEs (TEAEs) occurring in greater than 5% of patients treated at 105 mg/m² every 14 days and deemed by the investigators to be related to prexasertib treatment were fatigue (25.8%), nausea (11.7%), decreased appetite (8.5%), diarrhea (7.0%), and headache (5.6%).

2.1.2.6 Serious Adverse Events

Cumulatively, 360 serious adverse events (SAEs) have been reported in 193 patients in 6 Lilly-sponsored and 3 Investigator-sponsored monotherapy or combination studies up to 14 January 2017. In the 373 patients treated in the Lilly-sponsored studies, 289 SAEs in 159 patients have been reported. Out of 289 SAEs, 117 events were assessed as being possibly related to study drug treatment. The majority of drug-related events (76 events [65%]) were hematologic toxicities including neutropenia, leukopenia, anemia, febrile neutropenia, thrombocytopenia, or pancytopenia. Of the remaining related events, 14 were complications occurring in the setting of hematologic toxicity such as infections (10 events), bleeding events (3 events), or pyrexia (1 event).

2.1.2.7 Deaths

As of 13 January 2017, no patients had died due to adverse events (AEs) deemed related to study treatment. Please refer to the IB for comprehensive prexasertib background information.

2.2 Study Disease

In cancer cells, uncontrolled cell growth and sustained proliferative signaling can result in replication stress. Replication stress is associated with several genomic alterations that drive unbridled S phase entry, resulting in error prone replication, nucleotide or replication factor

[figure not shown]
depletion and the slowing or stalling of replication forks¹⁵⁻¹⁷. These genomic alterations include *MYC* amplification¹⁵, cyclin E gene (*CCNE1*) amplification¹⁸, and loss of the retinoblastoma protein (*Rb*)¹⁹. Additionally, mutations in the E3 ubiquitin ligase *FBXW7* can stabilize *MYC*, cyclin E, and other replication stress-inducing oncoproteins^{20,21}.

MYC amplification is involved broadly in many cancers; *MYC* over-expression results in increased proliferation, cellular survival and angiogenesis, promoting tumor growth²². High levels of *MYC* have been linked to both aggressive prostate and triple-negative breast cancer (TNBC)²³. *CCNE1* amplification is the most frequent amplified gene in ovarian serous carcinomas and is correlated with poor prognosis and primary treatment resistance. *CCNE1* amplification is also associated with disease progression and poor clinical outcome in breast, bladder, and colorectal carcinoma²⁴. *Rb* loss is associated with approximately 40% of TNBCs that harbor a p53 mutation (estimated to occur in > 80% of all TNBC patients)²⁵.

In addition to replication stress, uncontrolled cell cycle progression in cancer cells results in double strand DNA breaks. HR repair is essential for repair of this type of DNA damage and the maintenance of genomic stability and deficiency in HR repair is implicated in tumorigenesis. Mutations in HR associated genes have been identified in a number of cancers²⁶⁻³⁰. Germline or somatic mutations in HR genes, including *BRCA 1/2*, *RAD51C*, *RAD51D*, and *ATM*, are present in nearly 1/3 of all ovarian carcinomas (including both serous and non-serous histologies). Germline mutations among this group are frequently associated with familial forms of breast and pancreatic cancers^{30,31}.

2.3 Replicative Stress and HR Deficiency Cohort Rationale

Inhibitors of CHK1 have been shown to sensitize cells to DNA damaging agents and have been under development in combination with chemotherapy². However, there is recent interest in defining the monotherapy vulnerabilities of these agents. Emerging data suggest that when undergoing severe replication stress, cells require CHK1 for stabilizing replication forks³²⁻³⁵ and to promote homologous recombination (HR) repair via the phosphorylation and activation of HR associated proteins (e.g., *RAD51* and Fanconi anemia proteins) for repair of DNA strand breaks during replication^{3,36-38}, therefore inhibition of CHK1 may be lethal to these cells. In cells with HR deficiency, there is increased intrinsic DNA damage that activates the ATR-CHK1 pathway for checkpoint control. Inhibition of CHK1 in HR deficient cells will disrupt checkpoint control, allowing for continued cell cycle progression without DNA repair and resulting in mitotic catastrophe. Inhibition of CHK1 activity itself also leads to replication stress, with an increase in DNA replication initiation and an associated increase in RPA protein, single-stranded DNA formation, and DNA strand breaks^{9,39}. HR-deficient cells cannot faithfully repair such strand breaks, resulting in cell death. In addition, it has been shown that severe replication stress and HR repair deficiency are synthetically lethal⁴⁰. These observations suggest that cancer cells under replication stress or those with HR deficiency may be susceptible to CHK1 inhibitor monotherapy:

Clinical and preclinical studies support this hypothesis that CHK1 inhibition may be clinically relevant in patients with tumors exhibiting replication stress or HR deficiency.

2.5 Correlative Studies Background

Use of targeted therapies in patients with genomically complicated tumors presents a variety of confounding variables that could contribute to success or failure of the therapy. Correlative studies are designed to both enable better understanding of the possible reasons that prexasertib (LY2606368) may prove to be effective or ineffective in individual patients and to enable us to develop more effective targeting strategies in the future.

2.5.1 Collection of Fresh Tumor Tissue – Replicative Stress and HR Cohorts

In order to retrospectively explore the determinants of response and resistance to prexasertib, a mandatory pre-treatment fresh tumor biopsy will be obtained from the patients during Stage 1 of the 2-stage trial. The nine biopsies from both cohorts will be sufficient to demonstrate meaningful results, however will allow patients who are not amenable to biopsy or for whom a biopsy would pose significant risk to enroll on trial at the later stage.

Analysis of biopsy samples taken at distinct points enables addressing of key questions including the genomic lesions present in samples studied and their potential impact upon response following prexasertib therapy.

It is the anticipation that most patients on this study will have had their tumor genomically characterized by either the OncoPanel test at DFCI/BWH (a custom hybrid capture panel which via next-generation sequencing will identify mutations and copy-number alterations in cancer associated genes) or via another CLIA-certified method at the time of enrollment. A pre-

treatment tumor tissue sample will be subjected to WES at the Broad Institute Center for Cancer Precision Medicine. WES enables a comprehensive analysis of DNA mutation in human tumor samples. Gene expression profiling has been demonstrated to predict disease-free and overall survival in multiple cancers and guide future treatment decisions and biologic discovery⁵⁴⁻⁵⁶. WES will be performed to profile the HR proficiency of the tumor, and will involve up to 100 genes of interest in DNA repair in order to obtain the entire HR state. This will allow identification of further genomic alterations that may occur outside of the pre-set enrollment genetic alterations of these patients. The data obtained via WES will enable us to identify secondary alterations that may impact clinical response.

2.5.2 Collection of Blood – All Cohorts

Cell-free DNA (cfDNA) will be collected and analyzed for mutations associated with the replicative stress and HR deficiency pathways. Levels of tumor DNA will decline longitudinally over time if there is a response to the treatment administered. To further assess this concept, plasma will be collected from participants to evaluate whether circulating free plasma DNA declines with the administration of prexasertib and this information will be compared to clinical outcome.

3. PARTICIPANT SELECTION

3.1 Eligibility Criteria

Baseline evaluations are to be conducted within 14 days prior to start of protocol therapy, with the exception of the informed consent and baseline tumor imaging which may be obtained up to 28 days prior to the start of protocol therapy. Participants must meet the following criteria to be eligible to participate in the study:

- 3.1.1 Participants must have a pathologically confirmed advanced solid tumor for which standard therapy proven to provide clinical benefit does not exist or is no longer effective.
- 3.1.2 Participants must have one of the following (confirmed via targeted NextGen Sequencing using the DFCI/BWH OncoPanel or another CLIA-certified method):
 - For the replicative stress cohort: *MYC* amplification, *CCNE1* amplification, *Rb* loss, *FBXW7* mutation, or another genomic abnormality indicative of replicative stress as agreed upon with the principal investigator.
-OR-
 - For the HR deficiency cohort: genomic or somatic mutation in *BRCA1*, *BRCA2*, *PALB2*, *RAD51C*, *RAD51D*, *ATR*, *ATM*, *CHK2*, the Fanconi anemia pathway genes, or another genomic or somatic mutation in a known HR gene as agreed upon with the principal investigator.
-OR-
 - For enrollment to the *CCNE1* cohort: *CCNE1* amplification of 6-fold or greater.

Patients with borderline amplification levels may be considered following approval from the overall principal investigator.

- 3.1.3 Participants must have measurable disease, defined as at least one lesion that can be accurately measured in at least one dimension (longest diameter to be recorded for non-nodal lesions and short axis for nodal lesions) as ≥ 20 mm with conventional techniques or as ≥ 10 mm with spiral CT scan, MRI, or calipers by clinical exam. See **Section 11** for the evaluation of measurable disease.
- 3.1.4 Age ≥ 18 years. As no dosing or adverse event data are currently available in participants < 18 years of age, children are excluded from this study but will be eligible for future pediatric trials.
- 3.1.5 ECOG performance status < 2 (see **Appendix A**).
- 3.1.6 Participants must have adequate organ and marrow function as defined below:
- Absolute neutrophil count ≥ 1.5 K/uL
 - Platelet count ≥ 100 K/uL
 - Hemoglobin ≥ 9 g/dL (with or without transfusion support)
 - Total bilirubin $\leq 1.5 \times$ institutional upper limit of normal (ULN)
 - AST(SGOT)/ALT(SGPT) $\leq 2.5 \times$ institutional ULN, unless liver metastases are present and then $\leq 5 \times$ institutional ULN is acceptable
 - Serum creatinine $\leq 1.5 \times$ institutional ULN
- 3.1.7 Participants enrolling to the HR or replicative stress cohorts during Stage 1 must have disease that is amenable to biopsy and be willing to undergo a pre-treatment tumor biopsy.
- 3.1.8 The potential effects of prexasertib (LY2606368) use during pregnancy and lactation are not known. Nonclinical studies of prexasertib on pregnancy and fetal development have not been performed. To minimize any potential risks, men and women with reproductive potential should use medically approved contraceptive precautions during treatment and for 3 months following the last dose of prexasertib. Should a woman become pregnant or suspect she is pregnant while she or her partner is participating in this study, she should inform her treating physician immediately. Men treated or enrolled on this protocol must also agree to use adequate contraception prior to the study, for the duration of study participation, and for 3 months after completion of prexasertib administration.
- 3.1.9 Ability to understand and the willingness to sign a written informed consent document.
- 3.1.10 QTcF value of ≤ 470 msec on screening electrocardiogram (EKG).

3.2 Exclusion Criteria

Participants who exhibit any of the following conditions will not be eligible to participate

in the study:

- 3.2.1 Participants who have had chemotherapy, other investigational or biologic therapy, major surgery, or radiotherapy within 3 weeks (6 weeks for nitrosoureas or mitomycin C) prior to the planned first dose of prexasertib (LY2606368) therapy.
- 3.2.2 Participants who have not recovered to eligibility levels from prior toxicity or adverse events as a result of previous treatment prior to the study.
- 3.2.3 Participants who have received prior treatment with a CHK1 inhibitor.
- 3.2.4 Participants who have received prior radiation therapy to > 25% of the bone marrow.
- 3.2.5 Participants with known untreated brain metastases should be excluded from this clinical trial because of their poor prognosis and because they often develop progressive neurologic dysfunction that would confound the evaluation of neurologic and other adverse events. Participants with a history of brain metastases that have been treated, are no longer taking corticosteroids, and have been stable on imaging for at least one month following the end of treatment are permitted.
- 3.2.6 History of allergic reactions attributed to compounds of similar chemical or biologic composition to prexasertib.
- 3.2.7 Participants with a personal or family history of long QT syndrome.
- 3.2.8 Uncontrolled intercurrent illness including, but not limited to, ongoing or active infection, NYHA Class III/IV heart failure, unstable angina pectoris, cardiac arrhythmia, myocardial infarction within 3 months of enrollment, or psychiatric illness/social situations that would limit compliance with study requirements.
- 3.2.9 Pregnant or breastfeeding females. The potential effects of prexasertib use during pregnancy and breastfeeding are not known and prexasertib has the potential for teratogenic or abortifacient effects.
- 3.2.10 Known HIV-positive participants are ineligible because these participants are at increased risk of lethal infections when treated with marrow-suppressive therapy. Appropriate studies will be undertaken in HIV-positive participants when indicated.
- 3.2.11 Participants enrolling to the HR or replicative stress cohort during Stage 1 may not be on anticoagulant therapy unless the treating investigator has deemed it safe to temporarily hold to facilitate the pre-treatment tumor biopsy.

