4. REGISTRATION PROCEDURES

4.1 General Guidelines for DF/HCC Institutions

Institutions will register eligible participants in the Clinical Trials Management System (CTMS) OnCore. Registrations must occur prior to the initiation of protocol therapy. Any participant not registered to the protocol before protocol therapy begins will be considered ineligible and registration will be denied.

An investigator will confirm eligibility criteria and a member of the study team will complete the protocol-specific eligibility checklist.

Following registration, participants may begin protocol therapy. Issues that would cause treatment delays should be discussed with the Overall Principal Investigator (PI). If a participant does not receive protocol therapy following registration, the participant's registration on the study must be canceled. Registration cancellations must be made in OnCore as soon as possible.

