5.3.2 Hypersensitivity Reactions

Prexasertib mesylate monohydrate is formulated in Captisol® (sulfobutylether- β -cyclodextrin [SBECD]), which has been associated with allergic reactions. The etiology of the hypersensitivity reactions observed with prexasertib mesylate monohydrate is not known.

The patient should be monitored for signs and symptoms indicative of an infusion-related reaction for the duration of the infusion (including nausea, dizziness, chest pain, diaphoresis, flushing, decreased blood pressure, shortness of breath, hypoxia, and tachycardia). In the event of a suspected infusion reaction, institutional guidelines for managing infusion reactions should be followed. For subsequent infusions, premedication with diphenhydramine hydrochloride (dosing per investigator discretion) and/or other premedication as per institutional standards or investigator discretion may be administered. The infusion rate may also be decreased by 50 percent.

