8.1.2 Form

Prexasertib (LY2606368) for injection is supplied for clinical trial use as a lyophilized, yellow to white solid, in glass vials, and is composed of prexasertib mesylate monohydrate and the inactive ingredient sulfobutylether-β-cyclodextrin (Captisol). The drug product is available in two vial strengths containing either 20 mg or 40 mg of the base compound prexasertib. The 40 mg strength vial contains a 3% excess whereas the 20 mg strength vial contains a 5% excess to facilitate the withdrawal of the label amount (40 mg/vial and 20 mg/vial, respectively) for application with an appropriate device, such as an infusion set.

Reconstituting the 40 or 20 mg vial contents with 19 mL or 10 mL of water, respectively, yields a clear yellow solution with a concentration of 2 mg/mL of prexasertib, pH 4 to 6, and an osmotic pressure ratio of 344 mOsm.

The reconstituted solution may be diluted with dextrose 5% injection (D5W) prior to administration.

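### The only allergy exclusion (3.2.6) does not reach the excipient Captisol, which the protocol itself associates with allergic reactions, so no written criterion bars a participant with a known Captisol allergy

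*Combined protocol and SAP*

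**What the plan says.** Exclusion 3.2.6 rules out participants with a "History of allergic reactions attributed to compounds of similar chemical or biologic composition to prexasertib". No other inclusion or exclusion criterion deals with allergy.

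Section 5.3.2 makes two separate statements. The product is formulated in Captisol (sulfobutylether-β-cyclodextrin), "which has been associated with allergic reactions". The next sentence reads: "The etiology of the hypersensitivity reactions observed with prexasertib mesylate monohydrate is not known". The section then calls for monitoring for signs of an infusion-related reaction throughout the infusion, and refers to institutional guidelines if a reaction is suspected. After that come the optional measures: "For subsequent infusions, premedication with diphenhydramine hydrochloride (dosing per investigator discretion"), other premedication, or a halved infusion rate.

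Section 8.1.2 says the supplied product "is composed of prexasertib mesylate monohydrate and the inactive ingredient" Captisol, and that it comes as 20 mg and 40 mg vials.

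On how eligibility is decided, Section 4.1 says: "An investigator will confirm eligibility criteria and a member of the study team will complete the protocol-specific eligibility checklist". The checklist itself is not among the documents.

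**The concern.** An allergy exclusion is there to keep out people with a foreseeable risk of reacting to what they will be given. What they are given here is a drug and an excipient. The protocol names the excipient as having an association with allergic reactions, yet words its exclusion around the drug alone. Someone with a documented reaction to Captisol would meet none of the written exclusions, and nothing else in the protocol addresses that history before the first infusion.

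What is at stake is an avoidable infusion reaction in a participant whose history would have predicted it, and uneven screening if some investigators read 3.2.6 to include the excipient and others do not.

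**Working it through.** The plan states no figure on this point, so the check is textual.

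**1. What does 3.2.6 cover?** It covers compounds resembling prexasertib. Section 2.1 uses prexasertib as the name of the molecule (LY2606368 and its monomesylate monohydrate salt). Section 8.1.2 keeps the two parts of the product apart: prexasertib is the base compound and Captisol the inactive ingredient. On that usage a cyclodextrin is not a compound similar to prexasertib, and 3.2.6 does not reach it.

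**2. Does any other criterion reach it?** Criteria 3.1.1 to 3.1.10 and 3.2.1 to 3.2.11 contain no mention of Captisol, sulfobutylether-β-cyclodextrin, excipients or formulation. Exclusion 3.2.3 removes anyone previously treated with a CHK1 inhibitor, which already takes out people who reacted to prexasertib itself. It does nothing for someone who met Captisol in another product.

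**3. Is every participant exposed?** Yes. Section 8.1.2 describes one composition for the drug product and two vial strengths of it, so any infusion made from either strength contains Captisol.

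**4. Do the later sections close the gap?** Sections 4.1, 5.2 to 5.4 and 8.1 contain no screen for excipient allergy.

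| Provision in 5.3.2 | When it applies | Acts on a known Captisol allergy before the first dose? |
|---|---|---|
| Monitoring for signs of a reaction | Throughout the infusion | No |
| Institutional guidelines for infusion reactions | When a reaction is suspected | No |
| Premedication or slower rate (optional) | Infusions after a suspected reaction | No |

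**5. How many people?** The documents give no incidence for Captisol allergy and no rate for hypersensitivity to prexasertib. The nearest information is in Section 2.1.2.5, which lists the drug-related non-hematologic events seen in more than 5% of patients at 105 mg/m² every 14 days: fatigue, nausea, decreased appetite, diarrhea and headache. Hypersensitivity and infusion reaction are not on the list. Participants who arrive with an already documented Captisol allergy would presumably be a much smaller group. No number can be put on it.

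**Result.** Sections 5.3.2 and 8.1.2 together say that every infusion contains a component associated with allergic reactions. Section 3.2.6 does not ask about that component, and nothing else in the eligibility rules does.

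**The case against.** **The protocol does not blame Captisol for the reactions seen.** A reader might infer that Captisol is the only suspect and that 3.2.6 screens for the wrong thing. The documents do not support that. Section 5.3.2 reports hypersensitivity reactions with prexasertib mesylate monohydrate and says their cause is unknown. Captisol is the only component given a general association with allergy, but no cause is assigned to the observed reactions. This part of the objection stands. It is a reason to cover both components, since neither has been ruled out.

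**No one is obliged to infuse such a participant.** A reader might also infer that a person with a known Captisol allergy would be enrolled and treated. That does not follow. Medical history is taken at screening (Section 10), an investigator confirms eligibility (Section 4.1), and the checklist and investigator's brochure are not available here. The objection stands as far as the outcome goes: the documents show only that no written criterion bars the person. It does not repair the criterion, because a safeguard that depends on individual judgment is not a rule.

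**Composition might be read to include the formulation.** Section 8.1.2 does say the product "is composed of prexasertib mesylate monohydrate and the inactive ingredient sulfobutylether-β-cyclodextrin (Captisol"). The reading is possible but weak, because the same section separates the compound from the inactive ingredient, and 3.2.6 speaks of compounds similar to prexasertib rather than of the product. If sites could read it either way, that is a reason to clarify it.

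**Monitoring is already required.** True, and it applies to every infusion, not only after a reaction. It detects a reaction; it does not prevent one that the history would have predicted.

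**Conclusion.** The point holds as a gap in the eligibility wording. The sole allergy exclusion is narrower than its purpose requires, and it is out of step with what Sections 5.3.2 and 8.1.2 say about the product. It rests on the ordinary reading of 3.2.6, and on the assumption that a candidate could have met Captisol in some other product and reacted to it.

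Its size is unknown and probably very small.

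A reader might be tempted to carry it into the efficacy analysis, because a participant who does not complete cycle 1 may be replaced (Section 13) and is left out of the primary analysis (Section 13.3). The documents do not support that step. It would need a known allergy, enrollment despite it, and a reaction that stops cycle 1. Replacement could then restore the cohort count. The handling of participants who do not complete cycle 1 is a separate matter that applies to any early discontinuation. Sample size, power and the primary analysis are unaffected.

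**What to change.** The sponsor should reconcile Sections 3.2.6, 5.3.2 and 8.1.2. The simplest way is to add a phrase at the end of 3.2.6, such as *or to any component of the formulation, including sulfobutylether-β-cyclodextrin (Captisol)*, and to make the matching change to the eligibility checklist. Infusion-reaction handling in Section 5.3.2 need not change for this purpose.

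The cost is one phrase in the protocol, one checklist line and a negligible number of additional exclusions. It would still be useful: Section 13.2 gives a maximum of 50 participants, of whom 35 had yet to enroll as of 5 December 2017.
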